2.2 Safety population

The safety population includes all subjects who received the dose of study IIP.

A subject who received IIP but did not sign the informed consent will be included into the safety population.

2.3 Primary population

The co-primary analysis based on the primary efficacy endpoint to determine sstr2 positive percentage will use the ^{68}Ga -OPS202 screened population as the denominator. The co-primary analysis based on the primary efficacy endpoint to assess optimum imaging timing of the PET scan following ^{68}Ga -OPS202 injection will be performed on the sstr2 positive evaluable population.

In addition, as a supportive post-hoc analysis, the sstr2 positive prevalence may also be evaluated on the agreed optimum timepoint population.

All secondary and exploratory efficacy endpoints will be evaluated on the sstr2 positive evaluable population.

The assessment of safety and tolerability will be based on the safety population.

3 STATISTICAL METHODS

3.1 Statistical analysis strategy

The statistical analyses will be performed in accordance with International Conference on Harmonisation (ICH) E9 guideline [1] and will be based on the pooled data from the individual study sites, unless otherwise stated.

Statistical analyses will be performed by Covance Clinical Development SARL.

3.1.1 Primary efficacy endpoints

The co-primary efficacy endpoints are:

- (a) Percentage of subjects with sufficiently avid lesion(s) to be identified as a sstr2 positive lesion. (Avid is defined by the blinded readers at one of the acquisition timepoints as an easily identifiable lesion radiologically, where there has been clear focal uptake of ^{68}Ga -OPS202 and 1.5-fold or greater uptake than the non-tumoural liver and lung parenchyma).

- (b) Differences in the number of lesions detected by ^{68}Ga -OPS202 between the three PET acquisition timepoints (0.5, 1 and 2 hours), and reader interpretation of optimal image(s) in the primary breast lesions. The optimum image acquisition time could be one, two or all three acquisitions timepoints i.e. no noticeable difference between 0.5, 1 and 2 hours post infusion.

3.1.2 Secondary efficacy endpoints

Key Secondary Endpoint:

- (c) Differences in the number of lesions detected by ^{68}Ga -OPS202 between the three PET acquisition timepoints (0.5, 1 and 2 hours), and reader interpretation of optimal image(s) in nodular and metastatic lesions. Significant uptake of ^{68}Ga -OPS202 for the evaluation of a lesion is an avid lesion defined by the blinded readers at one of the acquisition timepoints as an easily identifiable lesion radiologically, where there has been clear focal uptake of ^{68}Ga -OPS202 and 1.5-fold or greater uptake than in the non-tumoural liver and lung parenchyma.
- (d) The SUV_{mean} and SUV_{max} in the primary lesion between each of the three timepoints, measured in the most avid lesions (using the ^{68}Ga -OPS202 scans). This is assessed by the tumour-to-background ratio in the primary tumour and each of the major anatomic sites (liver, lymph nodes, bone, lungs and brain). The background consists of non-tumoural liver parenchyma or aortic blood where sufficient liver is not available. Identification of lesions to be used will be made by one of the two primary readers.

Other Secondary Endpoints:

- (e) Differences in relative lesion counts as a ratio of the number of lesions detected by ^{68}Ga -OPS202 at 0.5, 1 and 2 hours post dose respectively, compared to the number of lesions assessed by standard-of-truth (descriptive analyses). The standard-of-truth is the ^{18}F -FDG-PET/CT scan images acquired at any time during the study period (including the Screening period). This will be calculated by (number of lesions detected by ^{68}Ga -OPS202)/(number of lesions detected by ^{18}F -FDG-PET).
- (f) Differences of absolute number of lesions between the three PET acquisition timepoints detected in each of the following anatomic sites:
- Lymph nodes
 - Liver
 - Axial/appendicular skeleton
 - Lungs
 - Brain
- (g) The primary and secondary endpoints will also be evaluated on a radioactivity dose/kg of body weight.

Exploratory Endpoints:

- (h) Preliminary diagnostic sensitivity of ^{68}Ga -OPS202 imaging of breast cancer expressing sstr2 positive by both subject-based and lesion-based analysis compared to standard-of-truth

- (i) SNR calculated from lesion-free volume of interest (VOI) in the liver: $SUV_{\text{mean}}/SUV_{\text{SD}}$ at the three PET acquisition timepoints
- (j) Estimated correlation in terms of number of avid lesions between ^{68}Ga -OPS202 PET at the agreed “optimum timepoint” and ^{18}F -FDG-PET
- (k) Estimated correlation between ^{68}Ga -OPS202 PET uptake and results of immunohistochemistry staining of sstr2 of the primary tumour.

3.1.3 Safety endpoints

The safety and tolerability of ^{68}Ga -OPS202 will be assessed throughout the study by evaluating AEs, clinically significant abnormalities in laboratory tests (serum chemistry, haematology, and urinalysis), vital signs measurements (including blood pressure and heart rate), physical examination findings and body weight measurements, ECG findings, relevant medical history and concomitant medication/therapies usage.

The following safety endpoints will be evaluated:

- Percentage of subjects experiencing at least one AE of any grade according to the National Cancer Institute - Common Terminology Criteria for Adverse Events (NCI-CTCAE) version 5.0, including any serious adverse events (SAEs) and suspected unexpected serious adverse reactions (SUSARs). All AEs will be coded using the Medical Dictionary for Regulatory Activities (MedDRA) system organ class (SOC) and preferred term (PT) (as per most recent version).
- Percentage of subjects experiencing at least one AE of grade ≥ 3 according to NCI CTCAE.
- Clinically significant changes in physical examination, vital signs, ECG and laboratory findings, which will be recorded by the investigator as AEs.

3.1.4 Multiplicity

No multiple testing will be performed in this study.

3.1.5 Significance testing and estimation

The statistical analysis of efficacy and safety is only descriptive, therefore no formal statistical significance testing will be performed.

3.2 Analysis methods

3.2.1 Efficacy

All efficacy analyses will be based on the centralised review of scans imaging performed under the responsibility of the ICL.

As specified in the description of each efficacy criterion thereafter, analysis will be based on PET/CT assessments for lesion count endpoints (absolute number of lesions, relative lesion count, image quality and diagnostic sensitivity) and on PET assessments alone for SUV related assessments.

The standard-of-truth (SOT) is the ^{18}F -FDG-PET/ceCT scan images acquired at any time during the study period (including the Screening period).

Due to decision of study premature termination, several analyses and/or outputs were removed.

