reconstitution. After QC sampling, the volume to be injected into the subject is withdrawn from the IIP vial, containing up to 45 µg OPS202. This volume is determined to obtain the target radioactivity dose at the time of administration, taking into account the decay of ⁶⁸Ga. All subjects will receive a single dose of IIP, with ⁶⁸Ga radioactivity dose of 150-200 MBq, as a slow i.v. bolus injected over 1 minute.

There are no fasting conditions, nor food restrictions that should apply when administering ⁶⁸Ga-OPS202 to the subject.

Duration of treatment: ⁶⁸Ga-OPS202 will be administered as a slow i.v. bolus injected over 1 minute once at Baseline/Day 1 (Visit 2).

Reference therapy, dose and mode of administration:

Comparator compound/placebo:

In this study, there is no comparison with a reference-imaging product. The primary statistical analyses will evaluate the differences (if any) between the three different scan acquisition timepoints of the ⁶⁸Ga-OPS202 PET.

Other treatments: Any medication and/or therapy taken or received by the subject during the study, other than the study IIP (⁶⁸Ga-OPS202), will be considered concomitant medication whether or not it is targeting the studied breast tumour. Concomitant treatments are to be prescribed, modified, or discontinued at the investigator's discretion. Subjects must be withdrawn from the study, but followed-up when possible for further data collection, if at least one of the protocol-prohibited medications/therapies (see above-mentioned eligibility criteria) is received by the subjects during the study period up to the end of the ⁶⁸Ga-OPS202 PET/CT scan at Visit 2.

Any addition, change, or discontinuation of concomitant medications should be documented as defined in the study protocol.

Criteria for evaluation (endpoints):

Efficacy:

The primary and secondary imaging endpoints will be read by third-party independent readers. Co-primary and secondary endpoints will be measured in the primary tumour and key organs consisting of liver, lymph nodes, bone, lungs and brain.

Co-primary efficacy endpoints and evaluation

- Percentage of subjects with sufficiently avid lesion(s) to be identified as a sstr2 positive lesion. (Avid is defined by the blinded readers at one of the acquisition timepoints as an easily identifiable lesion radiologically, where there has been clear focal uptake of ⁶⁸Ga-OPS202 and 1.5-fold or greater uptake than the non-tumoural liver and lung parenchyma).

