The Screening Visit (Visit 1) will be performed within 14 days prior to the ^{68}Ga -OPS202 administration. At Screening, after obtaining written informed consent, the investigator will collect all the information required to confirm the subject eligibility including medical and surgical history, physical examination and vital signs, laboratory tests (haematology, blood chemistry and urinalysis) and tumour histopathology if available. Tumour biopsy, which is not a prerequisite for inclusion, is routinely performed for confirmation and staging of the disease, as well as classification according to hormone receptor status and human epidermal growth factor receptor 2 (HER2) status. For the study, the collection of an archived tumour sample (a block is preferred over paraffin embedded slides) is required for the evaluation of sstr2 expression by immunohistochemistry staining.

[figure not shown]
Subjects' eligibility will be re-checked by the investigator at Baseline/Day 1 (Visit 2) before administration of the IIP. If eligibility is re-confirmed, the subject will receive one injection of ^{68}Ga -OPS202 followed by whole body PET acquisition at 0.5, 1 and 2 hours after the injection of the IIP. A single ceCT scan will be performed according to the site standard procedure for chest, abdomen, pelvis and brain. This can be acquired after either of the two PET scans (^{18}F -FDG-PET or ^{68}Ga -OPS202 post the 2-hour acquisition). Low-dose CT scans will be acquired with PET scans when necessary for attenuation correction.

Subjects may be hospitalised overnight upon completion of the ^{68}Ga -OPS202 PET/CT scans at the discretion of the investigator. All subjects (either hospitalised or not) will attend a consultation on Day 2 for vital signs and laboratory tests. Also an ^{18}F -FDG-PET scan and ceCT scan will be arranged if not already acquired.

An End of Study Visit (Visit 3) will take place on Day 14 (± 3 days), during which the investigator will collect the safety information required by the study protocol (see Criteria of safety evaluation below). At the end of Visit 3, the subject's participation in the study will end. For any adverse event (AE) emerging or worsening during the study that persists beyond Visit 3, the investigator will monitor the subject until the AE is resolved or considered stabilised.

Study design scheme is presented in Figure 1.

Figure 1 Study Design

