3.6 Study Duration

Subject participation in the study will include:

- Visit 1: a screening period up to 14 days prior to IIP administration
- Visit 2: a single i.v. injection of between 150 MBq to 200 MBq of ⁶⁸Ga OPS202 on Day 1 followed by PET acquisition at 0.5, 1 and 2 hours ±10 minutes post dosing,
- Visit 3: a follow-up visit at Day 14 (±3 days) for evaluation of safety.
Within the study an ¹⁸F-FDG-PET scan and also a ceCT scan must also be acquired.

The subject's participation in the study will be considered to have ended at the time of the last visit (Visit 3, at Day 14 ±3 days).

The overall duration of the study will be approximately 4 weeks for each subject. The study will be considered to have started when the first subject has provided signed informed consent.

The study will be considered to have ended after the last subject has completed the last follow up period in the study.

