*If insufficient tumour free liver is available for reference tissue, then aortic blood pool will be used as background.

The tumour-to-background ratio will be obtained using the mean of all lesions tumour-to-background ratios for each of the six following organs:

- Primary breast lesion
- Liver
- Lymph nodes
- Bone
- Lungs
- Brain.

Tumour-to-background ratio is a unit-less measure where a high tumour-to-background ratio indicates high effectiveness of $^{68}\text{Ga-OPS202}$ as a diagnostic agent, in a similar manner to SUV_{max} .

Individual values of the lesion SUV_{max} , lesion SUV_{mean} , SUV_{mean} of the subject's reference tissue and tumour-to-background ratio will be listed by subject, by each of the six organs and by PET acquisition timepoint.

Other Secondary Endpoints:

c) Relative lesion count

The relative lesion count is the ratio of the number of lesions detected by $^{68}\text{Ga-OPS202}$ at each of the three PET acquisition timepoints compared to the number of lesions assessed by standard-of-truth ($^{18}\text{F-FDG-PET}$ scan).

For each PET/CT assessment, this ratio will be computed as indicated below:

$$\text{Relative lesion count} = \frac{\text{Number of lesions detected by } ^{68}\text{Ga} - \text{OPS202}}{\text{Number of lesions detected by } ^{18}\text{F} - \text{FDG} - \text{PET}}$$

Relative lesion count will be computed over all lesions of all organs and for each of the following organs:

- Primary breast tumour (among all subjects with at least one lesion detected by ^{18}F -FDG-PET in primary breast tumour).
- Lymph nodes (among all subjects with at least one lesion detected by ^{18}F -FDG-PET in lymph nodes).
- Liver (among all assessed subjects with at least one lesion detected by ^{18}F -FDG-PET in liver).
- Axial/appendicular skeleton (bone) (among all assessed subjects with at least one lesion detected by ^{18}F -FDG-PET in bone).
- Lungs (among all assessed subjects with at least one lesion detected by ^{18}F -FDG-PET in lungs)
- Brain (among all assessed subjects with at least one lesion detected by ^{18}F -FDG-PET in brain).

For the per organ analysis, the relative lesion count will be:

- Equal to 0 if there is no lesion identified in the specific organ on ^{68}Ga -OPS202 scan.
- Missing if the numerator is missing (for example in case of non-readable ^{68}Ga -OPS202 PET scan at timepoint) with non-null denominator
- Not analyzed if there is no lesion identified in the specific organ on ^{18}F -FDG-PET scan.

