Listing of prior and concomitant non-drug therapies will be presented for the SOC, PT and verbatim text. The listing will be sorted by subject number, chronological start date, stop date, SOC, PT and verbatim text.

A frequency table of the number and percentage of subjects will be provided by SOC and PT on the safety population.

3.2.9.3 *Concomitant medications for breast cancer*

Concomitant medications for breast cancer will be coded using WHO-DD, version June 2016 or higher. Medications which started and stopped before study IIP administration are considered as prior medications for breast cancer.

Medications which started before study IIP administration but are continuing will be considered as both prior and concomitant medications for breast cancer.

Listings will be presented for the therapeutic class, PT and verbatim text. The listings will be sorted by subject number, chronological start date, stop date, therapeutic class, PT and verbatim text.

A frequency table of the number and percentage of subjects will be provided by therapeutic class and PT on the safety population.

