3.2.9.4 Concomitant surgical procedures

Concomitant surgical procedures will be coded using the MedDRA, Version 19.1 or higher. Surgical procedures which started after study IIP administration will be considered as concomitant surgical procedures.

Listings will be presented for the SOC, PT and verbatim text. The listings will be sorted by subject number, chronological start date, stop date, SOC, PT and verbatim text.

A frequency table of the number and percentage of subjects will be provided for concomitant surgical procedures by SOC and PT on the safety population.

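### The FDG standard-of-truth has no timing rule relative to treatment, so a relative lesion count may set a pre-treatment OPS202 scan against a post-treatment FDG scan

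*SAP*

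**What the plan says.** - **Reference scan.** SAP 3.2.1 defines the standard-of-truth as the FDG-PET/ceCT "scan images acquired at any time during the study period (including the Screening period"). SAP 3.1.2 (e) and Protocol 3.2.2.2 and 11.4.4 give the same open window.
- **Ratio.** SAP 3.2.1.2 c): "The relative lesion count is the ratio of the number of lesions detected by" OPS202 at each timepoint to the number seen on FDG, over all organs and by organ. An organ with no FDG lesion is not analysed. Counts of 35 or more are taken as 35.
- **Status at the OPS202 scan.** Protocol 4.2, exclusions 1 and 5, rules out a resected primary and any earlier breast cancer therapy. Eligibility is re-checked on Day 1 before dosing (Protocol 3.1, 5.2.2).
- **End of the bar on therapy.** Under Other treatments, the Protocol synopsis requires withdrawal if a prohibited therapy "is received by the subjects during the study period up to the end of the" OPS202 scan at Visit 2. Concomitant treatment is otherwise at the investigator's discretion, and the definition covers treatment aimed at the breast tumour.
- **Late FDG.** For Day 2, Protocol 3.1 says that the "FDG-PET scan and ceCT scan will be arranged if not already acquired". Participation ends with Visit 3 (Protocol 3.6): "Visit 3: a follow-up visit at Day 14 (±3 days) for evaluation of safety".
- **Treatment data.** SAP 3.2.9.3: "Concomitant medications for breast cancer will be coded using WHO-DD, version June 2016 or higher". SAP 3.2.9.4: "Surgical procedures which started after study IIP administration will be considered as concomitant surgical procedures". Both are listed by subject in order of start date.

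**The concern.** The numerator and denominator of the ratio are meant to describe the same disease in the same woman. The numerator is fixed on Day 1, in an untreated patient with the primary in place. The denominator has no such protection once the Visit 2 scan is over. No section requires FDG to precede treatment, limits the interval between the two scans, or excludes or flags a ratio whose FDG scan came after therapy or surgery.

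A ratio that rises because disease was removed or treated between scans would say nothing about OPS202. The relative lesion count survived the cuts made after early termination, and it is listed subject by subject, so a distorted value would stand as that woman's result. SAP 3.2.1.2 also says that the outputs for the secondary endpoints will inform the choice of imaging time.

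**Working it through.** The plan gives no figure on this point, so there is none to reproduce. The check has two parts: whether the rules permit the mismatch, and what it does to the ratio.

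**1. Do the rules permit it?**

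- An FDG scan taken before dosing is safe: exclusions 1 and 5 keep the woman untreated and unresected until then.
- After the Visit 2 scan the bar on therapy has lapsed, and FDG may still be outstanding.
- The last possible day in the study is Day 14 + 3 = Day 17, which is 17 − 1 = 16 days after dosing.
- Protocol 6.3 does not permit any radiopharmaceutical until 48 hours after the PET/CT. Read literally, this puts a post-dose FDG scan at about Day 3 or later, so the exposed window is about Day 3 to Day 17. (The same wording sits awkwardly with Protocol 5.2.1, which lists FDG among the screening procedures. The two should be reconciled.)

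The mismatch therefore needs two things together: FDG after Visit 2, and therapy or surgery before that FDG scan. The rules allow both.

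**2. Effect on the ratio**

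Let G be the OPS202 count at a timepoint, D the FDG count without treatment, and f the fraction of FDG lesions lost before the FDG scan. G is fixed.

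- Ratio: G/D becomes G/[D(1−f)], that is, it is multiplied by 1/(1−f).
- Difference between two timepoints: (G₁−G₂)/D is multiplied by the same 1/(1−f).

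The documents give no value for f, so a range is assumed:

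| f (assumed) | 1/(1−f) |
|---|---|
| 10% | 1/0.90 = 1.11 |
| 25% | 1/0.75 = 1.33 |
| 50% | 1/0.50 = 2.00 |

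**3. Illustration with assumed counts**

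Take OPS202 counts of 4 and 3 at two timepoints and five FDG lesions before treatment.

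| FDG lesions lost | Ratio, count 4 | Ratio, count 3 | Difference |
|---|---|---|---|
| 0 of 5 | 4/5 = 80% | 3/5 = 60% | 20 points |
| 1 of 5 | 4/4 = 100% | 3/4 = 75% | 25 points |
| 2 of 5 | 4/3 = 133% | 3/3 = 100% | 33 points |

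**4. Resection of the primary**

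Suppose FDG would show one primary lesion and three nodes, and OPS202 shows one and two. Before surgery the all-organ ratio is 3/4 = 75%. If only the primary is removed before FDG, the primary-breast ratio is 1/0 and is not analysed, while the all-organ ratio becomes 3/3 = 100%.

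**5. Where the factor does not apply**

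- All FDG lesions in an organ lost: the subject leaves that organ's ratio.
- Both counts still 35 or more: the ratio stays at 100%.

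**6. What does not move**

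- The three timepoints in a subject share one FDG denominator, so their order cannot change.
- The co-primary calculations in SAP 3.2.1.1 do not use FDG lesion counts.

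**The case against.** The case against has several parts.

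- **Likelihood.** The Protocol describes FDG as part of routine diagnosis and lists it at Visit 1. Day 2 is a catch-up. A woman is affected only if FDG is late and treatment starts first, and the documents do not show that any such woman exists. This stands: the number is unknown and may be zero.
- **Expectation of treatment.** A reader might infer from SAP 3.2.9.3 and 3.2.9.4 that the sponsor expects breast cancer treatment during follow-up. Those sections are coding and listing rules. The first also defines prior breast cancer medications, which exclusion 5 forbids, and the second covers any surgery. They show that such data would be recorded, not that treatment is foreseen.
- **Direction and size.** No document supports a fall in FDG lesion count within about 16 days of starting a drug. This stands, so f is only an assumption. Surgical removal of a lesion needs no such assumption.
- **Consequence.** The ratio is a descriptive, other secondary endpoint, now only listed. Sensitivity and the FDG correlation, which rest on the same reference, are no longer provided. This also stands and keeps the point small.
- **Traceability.** Assessment days (SAP 3.2.4) and treatment start dates are listed, so a careful reader could find an affected subject. True, but it means comparing separate listings, and no rule or flag prompts it.

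None of this supplies the missing timing rule.

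**Conclusion.** The gap is real and small. As written, the plan can pair a pre-treatment OPS202 count with a post-treatment FDG count for any woman whose FDG scan falls after Visit 2. If FDG lesions were lost in between, the relative lesion count (over all organs, or by organ where FDG lesions remain) and the size of its between-timepoint differences are inflated by 1/(1−f): 1.11 to 2.00 for assumed losses of 10% to 50%. If an organ loses all its FDG lesions, the subject drops out of that organ's ratio.

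Two stronger readings are tempting and not supported:

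- That resection of the primary inflates the primary-breast ratio. Where the primary is the only FDG lesion in the breast, SAP 3.2.1.2 c) makes that ratio not analysed. Any inflation shows only in the all-organ ratio, if other FDG lesions remain.
- That the open window could change which imaging time looks best. The shared denominator leaves the order of timepoints within a subject unchanged, and the co-primary calculations are untouched.

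The conclusion rests on the timing rules as written, a fixed OPS202 numerator, and an assumed f. The number of affected women cannot be derived from the documents. This is a cheap improvement to a descriptive listing, not an error that threatens a main result.

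**What to change.** In SAP 3.2.1.2 c), state that an FDG scan serves as standard-of-truth for the relative lesion count only if it was acquired before the first breast cancer therapy or surgery. For any other subject, flag her in the listing and either set the ratio to missing or show it separately as not valid.

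Two additions are needed:

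- **Population membership.** SAP 2.1.2 and 2.1.3 require an FDG scan for the sstr2 positive and evaluable populations, and the former is the numerator of the first co-primary percentage. Say explicitly that the new rule does not alter membership of either.
- **Change from protocol.** The open window is Protocol text, so record the rule in SAP section 5.

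The cost is a few sentences in the SAP and a comparison of the FDG date with treatment and surgery start dates that the SAP already lists. A few values may be lost from a descriptive secondary listing in a study with limited data; showing them separately instead of setting them to missing avoids even that. No study procedure or treatment decision changes.
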